10.5 Consenting

Patients will sign a consent form prior to study participation.

The consent will include willingness to allow acquisition and collation of blood, clinical and imaging data obtained on entry to the study and incorporate all other data from time of enrollment until the patient's completion/termination of the study including consent to future surveillance for long term (up to 3 years) clinical outcomes.

Exalenz Bioscience Ltd.	Last update on: May1, 2016
Study Title: Clinical Study of the BreathID [®] System to train the algorithm for the ¹³ C-Octanoate Breath Test with or without the ¹³ C-Methacetin Breath Test (OBT and MBT respectively) for correlation with histological findings of Non-Alcoholic Fatty Liver Disease (NAFLD)	Protocol No.: NASH-EX-1114
	Version: 1f
Document N^o: CSD00080	Page 30 of 61

10.6 Safety Termination of Subjects or Study

1. Withdrawal of patients from the study if they have a CTCAE Grade 3 or higher regardless of whether the event is attributed to the drug unless it is caused by an accident that could not reasonably be attributable to the drug (CTCAE: Common Terminology Criteria for Adverse Events Version 4.0).
2. Discontinuance of study, if ≥ 2 patients administered Octanoate / Methacetin develop the same CTCAE Grade 3 event or 1 patient develops a CTCAE Grade 4 or higher event due to one of the breath tests.

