 - i. Lipid profile and HbA1c - if not available within 6 months
 - j. Thyroid Panel - if not available within 12 months
 - k. Other assays where routinely practiced; (optional): Adiponectin + Leptin + IL6 + CK18, TNF α , C-peptide
4. OBT - ¹³C-Octanoate Breath Test (within 6 months of liver biopsy or within 1 month before liver biopsy) and ensuring MBT is feasible within 30 days but not less than 48 hours). If done on same day, OBT must be performed before the biopsy.
5. MBT - ¹³C-Methacetin Breath Test (within 30 days post OBT but not less than 48 hours). If done on the same day as the liver biopsy, the MBT must be performed before the biopsy.
6. Safety monitoring phone call 48 hours post last breath test. Any AEs reported that are possibly or probably related to the use of the product or related to the

Exalenz Bioscience Ltd.	Last update on: May1, 2016
Study Title: Clinical Study of the BreathID [®] System to train the algorithm for the ¹³ C-Octanoate Breath Test with or without the ¹³ C-Methacetin Breath Test (OBT and MBT respectively) for correlation with histological findings of Non-Alcoholic Fatty Liver Disease (NAFLD)	Protocol No.: NASH-EX-1114
	Version: 1f
Document N^o: CSD00080	Page 14 of 61

procedure will be followed until resolution and if laboratory work is done secondary to AEs and found abnormal, these tests will be followed until normalization or stabilization.

7. Follow-up Visit 18 months post last breath test performed: clinical evaluation (in person or telephone)
8. Follow-up Visit 36 months post last breath test performed: clinical evaluation (in person or telephone)
9. Any AEs reported that are possibly or probably related to the use of the product or related to the procedure within 36 months post last breath test performed or until subject termination will be followed until resolution and if laboratory work is done secondary to AEs and found abnormal, these tests will be followed until normalization or stabilization.

Rules of discontinuations (Subject and/or Study):

1. Withdrawal of patients from the study if they have a CTCAE (Common Terminology Criteria for Adverse Events) Grade 3 or higher regardless of whether the event is attributed to the drug unless it is caused by an accident that could not reasonably be attributable to the drug (CTCAE: Common Terminology Criteria for Adverse Events Version 4.0)

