10.7 Early Withdrawal from the Study

Patients, their relatives, their representatives or the patients' physician may withdraw the patient from the study at any time if they feel the study is not in the patients' best interest, or they may be withdrawn by the investigator or sponsor for safety, behavioral, or administrative reasons. All withdrawals must be fully documented.

If the patient withdraws from the study and also withdraws consent for the disclosure of future information, no further evaluations should be performed and no additional data should be collected. Previously acquired data will be analyzed. This will not have any effect on the treatment that the patient receives.

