11.4 Safety Endpoints

All Adverse Events recorded from the time of enrollment until the subject completes the protocol.

Any AEs reported that are possibly or probably related to the use of the product or related to the procedure within 36 months post last breath test performed or until subject termination will be followed until resolution and if laboratory work is done secondary to AEs and found abnormal, these tests will be followed until normalization or stabilization.

Exalenz Bioscience Ltd.	Last update on: May1, 2016
Study Title: Clinical Study of the BreathID [®] System to train the algorithm for the ¹³ C-Octanoate Breath Test with or without the ¹³ C-Methacetin Breath Test (OBT and MBT respectively) for correlation with histological findings of Non-Alcoholic Fatty Liver Disease (NAFLD)	Protocol No.: NASH-EX-1114
	Version: 1f
Document N^o: CSD00080	Page 32 of 61

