12.5 Visit 4: 48 safety hours phone call

1. 48 hours post the last breath-test (presumably MBT) a safety oriented phone call will be conducted.
2. All adverse events post OBT will be recorded until the subject completes the protocol.
NOTE: Any AEs reported that are possibly or probably related to the use of the product or related to the procedure within 36 months post last breath test performed or until subject termination will be followed until resolution and if laboratory work is done secondary to AEs and found abnormal, these tests will be followed until normalization or stabilization.
3. This visit determines the last safety reporting point to be reported in to the safety endpoint.

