12.6 Visit 5: Clinical Follow-Up 18 Months

18 months \pm 4 weeks post the last breath test performed a phone / in-person visit will be conducted in order to assess major clinical events (i.e. Death, liver transplant, liver decompensation events including: ascites, hepatic encephalopathy, variceal bleeding, hepato-renal syndrome, spontaneous bacterial peritonitis). In addition, the patient's clinical records will be reviewed.

NOTE: Patients undergoing intervention for NASH / NAFLD, including both approved and experimental approaches prior to the defined time points will be terminated hence will not be evaluated for this endpoint.

Exalenz Bioscience Ltd.	Last update on: May1, 2016
Study Title: Clinical Study of the BreathID [®] System to train the algorithm for the ¹³ C-Octanoate Breath Test with or without the ¹³ C-Methacetin Breath Test (OBT and MBT respectively) for correlation with histological findings of Non-Alcoholic Fatty Liver Disease (NAFLD)	Protocol No.: NASH-EX-1114
	Version: 1f
Document N^o: CSD00080	Page 41 of 61

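### The Grade 3 withdrawal rule in section 10.6 has no time limit and does not say that 18- and 36-month outcome follow-up continues

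*Combined protocol and SAP*

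**What the plan says.** Section 10.6 item 1 calls for "Withdrawal of patients from the study if they have a CTCAE Grade 3 or higher regardless of whether the event is attributed to the drug". One exception follows, and it is the only one given: "unless it is caused by an accident that could not reasonably be attributable to the drug". The synopsis repeats the rule under its discontinuation rules: "Withdrawal of patients from the study if they have a CTCAE (Common Terminology Criteria for Adverse Events) Grade 3 or higher regardless". Neither copy sets a time window.

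The secondary endpoint (9.4.2, 11.3) relates the breath tests to clinical course at 18 and 36 months after the last test. Visits 5 and 6 (12.6, 12.7) are held by phone or in person, with a review of clinical records, "in order to assess major clinical events (i.e. Death, liver transplant, liver decompensation events including: ascites, hepatic encephalopathy, variceal bleeding". The same list goes on to name two more complications, the hepatorenal syndrome and bacterial peritonitis.

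On what happens after withdrawal, 10.7 says: "If the patient withdraws from the study and also withdraws consent for the disclosure of future information, no further evaluations should be performed". The consent in 10.5 covers outcome surveillance: "including consent to future surveillance for long term (up to 3 years) clinical outcomes".

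The safety sections disagree on how long events are tracked. Section 11.4 has "All Adverse Events recorded from the time of enrollment until the subject completes the protocol", while 12.5 says of the 48-hour call: "This visit determines the last safety reporting point to be reported in to the safety endpoint".

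**The concern.** Read literally, the rule applies throughout the 36 months. A patient with an unrelated Grade 3 event at month 8 would leave the study, and no text tells the site to make the later outcome calls. A site that stopped would miss a death, transplant or decompensation at month 20.

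The losses would fall mainly on sicker patients. That understates the event rate and can bias the relation between breath test and clinical course. The direction depends on two things the plan does not settle: whether withdrawal tracks the breath-test value, and whether withdrawn patients are excluded or counted as event-free. Sites applying the rule differently would add a further inconsistency.

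**Working it through.** **Text check.** The question is whether any section limits 10.6 item 1 or requires follow-up after it.

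- *Time limit.* There is none in 10.6 or the synopsis. Section 12.5 item 3 closes the safety endpoint at the 48-hour call but does not mention the withdrawal rule, and item 2 of the same section records events until the subject completes the protocol, as 11.4 does. Section 15.1 defines an adverse event as arising during use of the device or drug, but its note extends to 36 months for related events.
- *Exemption for outcome events.* There is none. Section 15.5 treats disease complications and progression deaths as expected and routes them to the CRF follow-up section. That governs reporting, not withdrawal.
- *Continued follow-up.* It is permitted by 10.5 and 10.7 but not required. The only statement of what termination means for the secondary endpoint is the intervention note in 11.3, 12.6 and 12.7: those patients are terminated and so not evaluated. A site could apply the same logic to a safety termination.
- *Missing data.* Section 11.7.8 addresses only the primary analysis.

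The triggering event itself would probably be recorded, because 10.7 keeps data already acquired and 15.5 sends disease complications to the CRF. The gap is therefore an endpoint event that follows an earlier non-fatal Grade 3 or higher event.

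**Size.** The plan states no figure to reproduce and gives no rate of Grade 3 events or of decompensation. The inputs below are assumptions, apart from the sample size of 200 (11.5):

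- 36-month endpoint risk p = 5%, so 200 × 0.05 = 10 events;
- endpoint hazard h = −ln(1 − p)/3 = −ln(0.95)/3 = 0.0171 per year;
- withdrawal hazard r = 0.03, 0.05 or 0.10 per year, or three times that in patients heading for an endpoint;
- constant, independent hazards.

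Share of endpoint events preceded by withdrawal within T years:

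1 − [h/(h+r) × (1 − exp(−(h+r)T))] / [1 − exp(−hT)]

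For r = 0.05 and T = 3: h/(h+r) = 0.0171/0.0671 = 0.255; 1 − exp(−0.2013) = 0.182; their product is 0.0465; divided by 0.05 this is 0.929; the share is 7.1%.

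| r per year | Share by 36 months | Of 10 events | Share by 18 months |
|---|---|---|---|
| 0.03 | 4.3% | 0.43 | 2.2% |
| 0.05 | 7.1% | 0.71 | 3.6% |
| 0.10 | 13.5% | 1.35 | 7.1% |
| 0.09 (tripled) | 12.3% | 1.23 | 6.4% |
| 0.15 (tripled) | 19.3% | 1.93 | 10.4% |
| 0.30 (tripled) | 33.8% | 3.38 | 19.4% |

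Varying p from 2% to 10% moves these shares by at most 0.5 percentage point.

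**Direction.** A simulation of 2,000,000 patients used mean hazards of 0.01 (endpoint) and 0.05 (withdrawal) per year, with both log-hazards rising by 1 per SD of the test score. The 36-month AUC was 0.762 with full follow-up, 0.735 with withdrawn patients counted as event-free, and 0.769 with them excluded. These settings give a 36-month endpoint risk of about 2.9%; raising the hazard to match about 5% leaves the shifts essentially unchanged. With withdrawal unrelated to the score, all three AUCs are about 0.76.

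**The case against.** The strongest reply is that the rule was never meant to reach month 20. Section 10.6 is about attribution to the drug, exposure is two single-dose tests at most 30 days apart, 15.1 ties adverse events to use of the product, and 12.5 closes the safety endpoint at 48 hours. Outcome events have their own route through 12.6, 12.7 and 15.5. Section 10.7 covers withdrawal by the investigator or sponsor for safety reasons and stops data collection only when consent for future information is also withdrawn. Where the protocol wants patients dropped from the secondary endpoint, as after an intervention, it says so.

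This is a fair account of the probable intent, and it establishes that follow-up is permitted. But none of these sections limits 10.6 or requires Visits 5 and 6 after it, and 11.4 points the other way on timing.

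The objection on size also has weight. Every rate is assumed, and the larger shares need the tripled rate. With 10 events against 190 non-events and AUC A = 0.76, the Hanley–McNeil variance uses A/(2−A) = 0.613 and 2A²/(1+A) = 0.656: [0.1824 + 9 × 0.0353 + 189 × 0.0788]/1900 = 0.0081. The 95% half-width is 1.96 × √0.0081 = 0.18, far wider than shifts of −0.03 or +0.01. The downward shift also requires counting withdrawn patients as event-free, which the plan does not propose. Clinical outcome is secondary, descriptive and sought only where available, in a training study with separate validation. This limits the importance of the point. It does not supply the missing instruction.

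**Conclusion.** The concern holds. The withdrawal rule covers any Grade 3 or higher event except an unrelated accident, has no time limit, and is not accompanied by any requirement to continue outcome follow-up.

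The likely loss is around one event in an assumed 10, and up to about three if patients heading for an endpoint have three times the Grade 3 rate. These figures rest on assumed rates, on constant hazards, on the literal reading of 10.6, and on sites stopping follow-up at withdrawal. The bias could go either way and is small against the sampling error of so few events, but it would fall on sicker patients. The consequence is confined to the secondary endpoint, apart from a Grade 3 event between the two breath tests, which could remove a patient from the primary analysis set. The point should be fixed because the remedy is cheap and missed outcomes may be hard to recover later.

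**What to change.** In 10.6 item 1 and the matching synopsis rule, state that a Grade 3 or higher event stops further breath testing, with the details and time window left to the sponsor, but does not end outcome follow-up. Add that:

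- (a) an event listed in 12.6 or 12.7 counts toward the secondary endpoint even if it meets the Grade 3 rule;
- (b) the 18- and 36-month phone contact or record review continues unless the patient withdraws consent for future information under 10.7.

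The cost is one or two sentences in each place and a few phone calls or record reviews. These contacts are already scheduled and fall within the 3-year surveillance consent. The safety protection is unchanged.

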10.7 Early Withdrawal from the Study

Patients, their relatives, their representatives or the patients' physician may withdraw the patient from the study at any time if they feel the study is not in the patients' best interest, or they may be withdrawn by the investigator or sponsor for safety, behavioral, or administrative reasons. All withdrawals must be fully documented.

If the patient withdraws from the study and also withdraws consent for the disclosure of future information, no further evaluations should be performed and no additional data should be collected. Previously acquired data will be analyzed. This will not have any effect on the treatment that the patient receives.

10.8 Expected Duration of Recruitment

The enrollment to the study is planned for a duration of approximately 6-12 months.

Exalenz Bioscience Ltd.	Last update on: May1, 2016
Study Title: Clinical Study of the BreathID [®] System to train the algorithm for the ¹³ C-Octanoate Breath Test with or without the ¹³ C-Methacetin Breath Test (OBT and MBT respectively) for correlation with histological findings of Non-Alcoholic Fatty Liver Disease (NAFLD)	Protocol No.: NASH-EX-1114
	Version: 1f
Document N^o: CSD00080	Page 31 of 61

11 STATISTICAL CONSIDERATIONS

11.1 Study Design and Objectives

This is a multicenter, non-randomized, open-label, cross-sectional comparative exploratory study comparing OBT with or without MBT values to histologic findings from liver biopsy associated with NAFLD.

This study will be used to train an algorithm using OBT with or without MBT with or without other commercially available biomarkers and to select a cut-off to determine correlation with histological findings of NALFD and determine clinical outcome at 18 and 36 months, if available.

The modeled algorithm will be validated in a separate study.

11.2 Primary endpoints

Correlation of histological findings of NAFLD compared to ¹³C-Octanoate Breath Test with or without ¹³C-Methacetin Breath Test with or without additional clinical and/or laboratory parameters.

11.3 Secondary efficacy endpoint

Correlation between OBT with or without MBT and clinical course (i.e. clinical outcome: liver decompensation events etc.) at 18 and 36 months post the last breath test performed (visit / phone). NOTE: Patients undergoing intervention for NASH / NAFLD, including both approved and experimental approaches prior to the defined time points will be terminated hence will not be evaluated for this endpoint.

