3 PROTOCOL SYNOPSIS

Protocol Title:	Clinical Study of the BreathID [®] System to train the algorithm for the ¹³ C-Octanoate Breath Test with or without the ¹³ C-Methacetin Breath Test (OBT and MBT respectively) for correlation with histological findings of Non-Alcoholic Fatty Liver Disease (NAFLD)
Protocol Number:	NASH-EX-1114
Version and Date:	v 1f, May1, 2016
Investigational subject:	Biopsy characteristics of patients suspected of Non-Alcoholic Fatty Liver Disease (NAFLD)
Investigational Product	BreathID [®] System together with ¹³ C-labeled Octanoate and ¹³ C-labeled Methacetin
Primary Objective:	The primary objective of the study is to develop an algorithm based on OBT with or without MBT with or without additional clinical and/or laboratory parameters, and its cut-off to correlate with histological findings of NAFLD.
Primary Endpoint:	Correlation of histological findings, as assessed by a central reader, of NAFLD compared to ¹³ C-Octanoate Breath Test with or without ¹³ C-Methactin Breath Test with or without additional clinical and/or laboratory parameters
Secondary Endpoint:	Correlation between OBT±MBT and clinical course (i.e. clinical outcome: liver decompensation events etc.) at 18 and 36 months post the last breath test performed (visit / phone). NOTE: Patients undergoing intervention for NASH / NAFLD, including both approved and experimental approaches prior to the defined time points will be terminated hence will not be evaluated for this endpoint.
Safety Endpoints:	Safety will be assessed by reviewing all adverse and serious adverse events occurring in all subjects enrolled from the time of enrollment until the subject completes the protocol.

Exalenz Bioscience Ltd.	Last update on: May1, 2016
Study Title: Clinical Study of the BreathID [®] System to train the algorithm for the ¹³ C-Octanoate Breath Test with or without the ¹³ C-Methacetin Breath Test (OBT and MBT respectively) for correlation with histological findings of Non-Alcoholic Fatty Liver Disease (NAFLD)	Protocol No.: NASH-EX-1114
	Version: 1f
Document N^o: CSD00080	Page 10 of 61

Any AEs reported that are possibly or probably related to the use of the product or related to the procedure within 36 months post last breath test performed or until subject termination will be followed until resolution and if laboratory work is done secondary to AEs and found abnormal, these tests will be followed until normalization or stabilization.

Study Design:

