9.4.2 Secondary efficacy endpoint

Correlation between OBT with or without MBT and clinical course (i.e. clinical outcome: liver decompensation events etc.) at 18 and 36 months post the last breath test performed (visit / phone).

NOTE: Patients undergoing intervention for NASH / NAFLD, including both approved and experimental approaches prior to the defined time points will be terminated hence will not be evaluated for this endpoint.

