9.5 Safety Endpoints

Safety will be assessed by assessing all adverse and serious adverse events occurring in all subjects enrolled from the time of enrollment until the subject completes the protocol.

Any AEs reported that are possibly or probably related to the use of the product or related to the procedure within 36 months post last breath test performed or until subject termination will be followed until resolution and if laboratory work is done secondary to AEs and found abnormal, these tests will be followed until normalization or stabilization.

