12.7 Visit 6: Clinical Follow-Up 36 Months

36 months \pm 8 weeks post the last breath test performed a phone / in-person visit will be conducted in order to assess major clinical events (i.e. Death, liver transplant, liver decompensation events including: ascites, hepatic encephalopathy, variceal bleeding, hepato-renal syndrome, spontaneous bacterial peritonitis). In addition, the patient's clinical records will be reviewed.

NOTE: Patients undergoing intervention for NASH / NAFLD, including both approved and experimental approaches prior to the defined time points will be terminated hence will not be evaluated for this endpoint.

NOTE: Any AEs reported that are possibly or probably related to the use of the product or related to the procedure within 36 months post last breath test performed or until subject termination will be followed until resolution and if laboratory work is done secondary to AEs and found abnormal, these tests will be followed until normalization or stabilization.

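### The 18- and 36-month clinical-outcome endpoint drops patients with an earlier NASH/NAFLD intervention even when a listed event came before that intervention

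*Combined protocol and SAP*

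**What the plan says.** Section 9.4.2 defines the secondary endpoint as "Correlation between OBT with or without MBT and clinical course (i.e. clinical outcome: liver decompensation events etc.") at 18 and 36 months after the last breath test. Sections 12.6 and 12.7 name what is assessed at those contacts; in 12.6 it is "major clinical events (i.e. Death, liver transplant, liver decompensation events including: ascites, hepatic encephalopathy, variceal bleeding, hepato-renal syndrome, spontaneous bacterial peritonitis").

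Section 11.3 then removes patients with an intervention for NASH or NAFLD, "including both approved and experimental approaches prior to the defined time points will be terminated hence will not be evaluated for this endpoint". The same note stands in the synopsis (section 3: such patients "will be terminated hence will not be evaluated for this endpoint"), in 9.4.2, and separately under Visit 5 (12.6) and Visit 6 (12.7). None of the five adds an exception for an event that came first, or says that follow-up is censored at the intervention. The term for the triggering intervention is not defined.

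**The concern.** The secondary aim is to relate the breath test to disease course. Restricting that to untreated course is a reasonable choice, but it does not require discarding events that happened before treatment. Under the note, whether an observed event counts depends on something that happened after the breath test and after the event itself.

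At stake are valid events in an endpoint that is likely to have few of them. If intervention is more likely after an event, and more so at some breath-test values than at others, the estimated association could also shift.

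**Working it through.** **Does any other section rescue the earlier event?**

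- Section 10.7 says that data already acquired will be analysed. That sentence stands in the paragraph on withdrawn consent. It does not mention termination because of an intervention, and it does not override the specific note.
- Section 11.7.8 covers missing OBT, MBT or biopsy results in the primary analysis only.
- Section 11.6 defines the analysis sets without reference to this endpoint.

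**Which results are lost?** The note refers to the defined time points and is repeated under each visit, so it is best read per time point.

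- Event at month 10, intervention at month 11: not evaluated at 18 or at 36 months.
- Event at month 10, intervention at month 24: counted at 18 months, dropped at 36.
- Event-free, intervention at month 24: the 18-month result stands; not evaluated at 36.

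**Would the event be on record?** Partly. Section 9.5 covers adverse events "occurring in all subjects enrolled from the time of enrollment until the subject completes the protocol", section 11.4 has the same period, section 15.5 sends disease complications to the follow-up part of the CRF, and section 10.5 obtains "consent to future surveillance for long term (up to 3 years) clinical outcomes". But the statement that the patient's "clinical records will be reviewed" belongs to the 18- and 36-month visits, which a terminated patient does not reach. Section 12.5 also makes the 48-hour call the last reporting point for the safety endpoint, which conflicts with 9.5 and 11.4.

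**Illustrative size.** The plan gives no figure for this endpoint; section 11.5 sizes the study on the AUC alone. All inputs here are assumptions: 100 high-score and 100 low-score patients with 36-month event risks of 12% and 3%, hence 12 + 3 = 15 events.

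- Events kept under the rule = 100 × risk × (1 − share of event patients excluded), summed over the two groups.
- Events recovered = f × (15 − events kept), where f is the share of excluded event patients whose event came first.
- 95% CI factor of the rate ratio = exp(1.96 × √(1/eH + 1/eL)), with eH and eL the events counted per group.

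| Excluded | Rule: events (high + low) | CI factor | Fix, f = 0.5: events (high + low) | CI factor |
|---|---|---|---|---|
| 0% | 15 (12 + 3) | 3.54 | 15 (12 + 3) | 3.54 |
| 10% | 13.5 (10.8 + 2.7) | 3.79 | 14.25 (11.4 + 2.85) | 3.66 |
| 20% | 12.0 (9.6 + 2.4) | 4.11 | 13.5 (10.8 + 2.7) | 3.79 |
| 40% | 9.0 (7.2 + 1.8) | 5.12 | 12.0 (9.6 + 2.4) | 4.11 |

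Exclusion may also depend on score or outcome. If 5% of event patients are excluded, 14.25 events are kept and f = 0.5 recovers 0.5 × 0.75 = 0.4. In a deliberately extreme case (70% of high-score and 30% of low-score event patients), 3.6 + 2.1 = 5.7 are kept and 0.5 × 9.3 = 4.7 are recovered. At f = 0 nothing is recovered.

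*Lower base risk.* With 4% against 1% (5 events), 20% excluded and f = 0.5, the rule keeps 3.2 + 0.8 = 4 events and the fix counts 3.6 + 0.9 = 4.5. The factor moves from 11.6 to 10.1.

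**Bias.** Assume risks of 8% and 2% (true risk ratio 4.0) and 10% of event-free patients excluded.

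- 50% of event patients excluded in both groups: [4/(4 + 82.8)] / [1/(1 + 88.2)] = 4.11.
- 50% excluded in the high-risk group and 10% in the low-risk group: [4/86.8] / [1.8/(1.8 + 88.2)] = 2.30.

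The answer depends on rates that the documents do not give.

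**Why adding back the events alone is not enough.** In the 12% group, with 20% excluded and f = 0.5, adding back the 1.2 earlier events while dropping everyone else who was treated gives (9.6 + 1.2)/(80 + 1.2) = 13.3%, against an assumed 12%. Treated patients who were event-free must contribute their time up to the intervention.

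**The case against.** The strongest case against is that little turns on this. The endpoint is secondary, the study is exploratory (11.1) and its analyses descriptive (11.7.1), outcome is sought only where available (sections 8 and 11.1), and no sample size or success criterion rests on it (11.5, 11.7.5). An intervention for NASH or NAFLD reads as disease-directed therapy, and nothing shows how often that follows decompensation. The assumed base risk has no source in the documents, and the gain shrinks with it. A time-to-event analysis also differs from a correlation at two time points. All of this limits the consequence. None of it supplies a reason to discard an outcome that was observed before treatment.

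A reader might infer four stronger things that the documents do not support:

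- *An 18-month result is lost if the intervention comes between months 18 and 36.* An intervention at month 24 is not prior to month 18, and the note is repeated visit by visit. A confirming phrase is enough.
- *The association is biased in a known direction.* The examples above give a nearly unchanged ratio or a much smaller one, depending only on assumed rates.
- *The gap is purely one of definition because the data will be there anyway.* Terminated patients miss the scheduled record reviews, and the sections on the safety reporting period disagree.
- *The primary endpoint is affected.* The comparison with histology does not use this rule.

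**Conclusion.** The point stands on the text: listed events that precede an intervention are not counted at any later time point, and no other section restores them. The established consequence is that valid untreated-course events are discarded, with some loss of precision. In the illustration with 15 events and f = 0.5, the rule costs between 0.4 and 4.7 recoverable events, the upper end coming from the extreme pattern. Every one of these figures rests on assumed event risks, exclusion shares and ordering of event and intervention. The gain falls with lower event rates and is zero if no event comes first. Bias is possible but cannot be sized or signed. The change is worth making because it is cheap; the effect is limited to one secondary endpoint.

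**What to change.** Replace the exclusion, for this endpoint, with a rule of this kind: listed events before the intervention date are counted; patients who are event-free at the intervention contribute follow-up up to that date and are then censored. Time to first event against the breath-test score is one suitable analysis. Add a phrase confirming that an 18-month result obtained before a later intervention is kept.

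Because terminated patients do not reach the 18- and 36-month contacts, record the intervention date, and any earlier listed event with its date, from the clinical records at the moment of termination. Reconcile section 12.5 with 9.5 and 11.4 on the reporting period. Define the triggering intervention for this endpoint, and state whether liver transplant, already a listed outcome in 12.6 and 12.7, counts in the analysis as an event rather than as an excluding intervention.

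The cost is protocol and SAP wording, plus one record check per terminated patient. No new visit and no follow-up after the intervention are needed. The remaining weakness is that censoring assumes the intervention is unrelated to later risk, which should be stated with the results.
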